**9.4.2.1 Adverse events and Serious Adverse Events**

Treatment-emergent adverse events are defined as AEs that first occurred or worsened in severity after the first administration of study treatment.

Adverse events will be coded using the Medical Dictionary for Regulatory Activities. For each study treatment, numbers of TEAEs and incidence rates will be tabulated by preferred term and system organ class.

Treatment-emergent AEs by maximum severity, TEAEs by relationship to study treatment, SAEs, TEAEs leading to death, and TEAEs leading to discontinuation of study treatment will be

tabulated for each treatment arm. Commonly occurring TEAEs, [REDACTED] in either treatment arm, will be summarized using descriptive statistics.

The safety of tildrakizumab will be evaluated by and reported as the percentage of subjects for the following TEAEs:

- Incidence, seriousness and severity of all AEs, death cases and discontinuations from the study.
- Percentage of subjects with severe infections, defined as any infection meeting the regulatory definition of a serious adverse event, or any infection requiring IV antibiotics whether or not reported as a serious event as per the regulatory definition.
- Percentage of subjects with malignancies (excluding carcinoma in situ of the cervix).
- Percentage of subjects with non-melanoma skin cancer.
- Percentage of subjects with melanoma skin cancer.
- Percentage of subjects with MACE [REDACTED]
- Percentage of subjects with study treatment-related hypersensitivity reactions (eg, anaphylaxis, urticaria, angioedema, etc).
- Percentage of subjects with injection site reactions (eg, pain, erythema, edema, etc).

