- 238 • To assess the effect of tildrakizumab on IGA (scalp only), Scalp Itch NRS, PASI,
239 PGA-S (whole body), and IGA mod 2011 (whole body), at week 12 and other
240 measured time points through Week 52.
- 241 • To assess the time to response
- 242 • To assess the efficacy of tildrakizumab in the improvement of scalp itch as measured
243 by the proportion of subjects achieving a 4-point reduction in Scalp Itch Numeric
244 Rating Scale (NRS) score from Baseline at Week 16 compared with placebo
- 245 • To assess the efficacy of tildrakizumab in the treatment of moderate to severe
246 psoriasis (entire body including scalp) compared with placebo as measured by
247 Psoriasis Area and Severity Index (PASI), IGA mod 2011 (whole body), Physician
248 Global Assessment for skin (PGA-S) score (whole body), and total body surface area
249 (BSA) involvement at Week 16.

250 **2.3 Exploratory Objective**

251 The exploratory objective of this study is:

- 252 • To assess the effect of tildrakizumab on Quality of Life measured by: Dermatology
253 Life Quality Index (DLQI).

254 **3 OVERALL STUDY DESIGN AND TREATMENT PLAN**

255 The overall study design and treatment plan are described in Sections 4.1 of Clinical Protocol
256 TILD-18-20 [REDACTED]. A brief overview is included below.

257 This is a multicenter, randomized, double-blind, placebo-controlled Phase 3 study to assess
258 the efficacy and safety of tildrakizumab in the treatment of moderate to severe psoriasis of
259 the scalp. The study will enroll approximately 214 subjects with moderate to severe psoriasis

260 of the scalp. Eligible subjects will be randomized to 1 of the 2 arms [REDACTED] Arm A:
261 Tildrakizumab 100 mg, subcutaneous (SC) (n=107) and Arm B: Placebo, SC (n=107).

262 The study will comprise 3 parts:

263 **PART 1: Double-blind Placebo-controlled (Day 1 to Week 16)**

264 After a Screening Period of up to 28 days and on Day 1, all eligible subjects will be
265 randomized 1:1 to receive either tildrakizumab 100 mg or placebo administered by SC
266 injection [REDACTED]. Subjects should receive the first dose of study
267 treatment within 24 hours of randomization. The treatment period for the double-blind
268 placebo-controlled part of the study is 16 weeks. All assessments of efficacy and safety
269 before or on the date of injection at Week 16 [REDACTED]
[REDACTED] are considered in PART 1.)

271 **PART 2: Double-blind Active Treatment Extension (Week 16 to Week 52)**

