763 **4.9.3.3 Interim Analyses (IA), Data Monitoring and Primary Results Reporting**

764 Following the last subject's Week 16 visit, the IA (primary analysis) will be conducted on
765 available data to evaluate efficacy and safety.

[REDACTED]

[REDACTED]

[REDACTED]

[REDACTED]

[REDACTED]

795 **4.9.3.4 Multicenter Studies**

796 Descriptive summaries of the primary and key secondary efficacy endpoints will be presented
797 for each individual study center to evaluate potential heterogeneity across sites.

[REDACTED]

[REDACTED]

[REDACTED]

[REDACTED]

[REDACTED]

810 **4.9.4 Tabulation of Individual Response Data**

811 All efficacy variables will be listed by subject.

812 **4.9.5 Drug Dose, Drug concentration, and Relationships to Response**

813 Not applicable.

814 **4.9.6 By-Subject Displays**

815 No individual subject profile data will be produced.

[REDACTED]

820 **4.10 Safety Analysis**

821 The safety and tolerability of the study drugs will be evaluated by reported adverse events
822 (AEs), physical examinations, electrocardiogram results (ECGs), vital signs, laboratory test
823 results (Hematology, Biochemistry, and Urinalysis), and Columbia-Suicide Severity Rating
824 Scale (C-SSRS).

825 All safety summaries will be based on the Safety Analysis Set.

826 Following reporting of interim Week 16 results, a group comprising formerly placebo-treated
827 subjects who migrate to tildrakizumab 100 mg for the remainder of the study will be
828 identified for reporting at the end of the study.

829 **4.10.1 Adverse Events**

830 The incidence of treatment-emergent AEs (TEAE) will be summarized and tabulated by
831 treatment group, MedDRA (Version 24.0 or higher) System Organ Class (SOC) and
832 Preferred Term (PT). A TEAE is defined as an AE that first occurred or worsened in severity
833 after the first administration of study treatment.

834 Several occurrences of the same AE in one subject will be counted once at the worst severity
835 grade. [REDACTED]
[REDACTED]

837 The relationship of each AE to the study drug will be grouped as related (definitely, probably,
838 possibly related) or unrelated (unlikely to be related, unrelated). Several occurrences of the
839 same AE in one subject will be counted once and the one with the closest relationship to
840 study medication will be counted. If an AE is missing the relationship to study medication,
841 the event will be assumed to be related to study drug for analysis and summarization.

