[REDACTED]

[REDACTED]

848 Non-TEAEs will be listed only and will not be included for analysis and summarization.

849 All AEs will be presented in a by-treatment and by-subject listing, detailing the verbatim
850 term, SOC, PT, application site reaction or not, related to study indication or not, start date,
851 stop date, time since most recent dose of IP, severity, outcome, relationship to study drug,
852 action taken regarding study drug, action taken to treat AE, seriousness and criteria for
853 seriousness. Serious AEs (SAEs) and TEAEs leading to study medication discontinuation,
854 AEs of Special Interest (AESI), and events of clinical interest (ECI) will also be presented in
855 separate listings.

856 An AE profile for the Safety Analysis Set will be provided for Part 1, Parts 2 and 3, and
857 overall, which summarizes the subject incidence, by treatment received for the following
858 information:

- 859 • Any TEAEs;
- 860 • Non-TEAEs;
- 861 • Drug-related TEAEs;
- 862 • Any TEAEs with an outcome of death;
- 863 • Treatment-emergent SAEs;
- 864 • Drug-related treatment-emergent SAEs;
- 865 • TEAEs leading to discontinuation of study medication;
- 866 • Drug-related TEAEs leading to discontinuation of study medication;

- 867 • Any AEs of special interest, including:
868 ○ Injection site reactions
869 ○ Severe infections
870 ○ Malignancies (excluding carcinoma in situ of the cervix).
871 ○ Non-melanoma skin cancer
872 ○ Melanoma skin cancer
873 ○ Major Adverse Cardiovascular Events (MACE)
874 ○ Study treatment-related hypersensitivity reactions.

[REDACTED]

[REDACTED]

891 The number and percentage of subjects with TEAEs will be summarized for each treatment
892 arm and/or in total by SOC and PT. Drug-related TEAEs, TEAEs leading to discontinuation
893 of study drug, drug-related TEAEs leading to discontinuation of study drug, treatment-
894 emergent SAEs, and drug-related treatment-emergent SAEs will be summarized in the same
895 manner. For these summaries, subjects with multiple AEs will be counted only once per SOC
896 and PT.

897 TEAEs by maximum severity and TEAEs by relationship to study treatment, and commonly
898 occurring TEAEs, i.e., those that occur in [REDACTED] of the subjects in either treatment arm,
899 will be summarized by SOC and PT by treatment received in Part 1, Parts 2 and 3, and
900 overall.

901 Injection site reactions will be described in a by-subject listing and may be summarized
902 separately if deemed necessary.

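### Overall adverse event tables: crude percentages by treatment received can set about 16 weeks of placebo beside 56 to 72 weeks of tildrakizumab, so the columns should be defined and exposure-adjusted rates added

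*SAP*

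**What the plan says.** SAP 4.10.1 plans the profile in three periods: "An AE profile for the Safety Analysis Set will be provided for Part 1, Parts 2 and 3, and" then "overall, which summarizes the subject incidence, by treatment received for the following" list of event types, which includes the adverse events of special interest (AESIs). The tables by maximum severity, by relationship and for common TEAEs use the same grouping and the same three periods. For the SOC and PT tables, "The number and percentage of subjects with TEAEs will be summarized for each treatment" arm and/or in total, with each subject counted once per term.

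Protocol 9.4.2.1 uses the same kind of measure: "The safety of tildrakizumab will be evaluated by and reported as the percentage of subjects for the following TEAEs". It also mentions incidence rates by preferred term and system organ class, without giving a denominator. Under SAP 2.1, the primary safety objective covers 52 weeks.

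Three other places bear on how an overall table would look:
- SAP 6.1.4 orders the columns as placebo, tildrakizumab 100 mg and, if applicable, total.
- SAP 6.1.5 makes the default denominator of every percentage the subjects with an observation, not time.
- SAP 4.10 adds a group: "Following reporting of interim Week 16 results, a group comprising formerly placebo-treated" subjects who move to tildrakizumab, to be identified for end-of-study reporting.

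SAP 3 sets Part 1 as Day 1 to Week 16, Part 2 as Week 16 to 52 and Part 3, without study treatment, as Week 52 to 72. Placebo subjects switch at Week 16.

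**The concern.** A crude percentage of subjects with an event rises with the length of observation. By design, placebo observation ends at about Week 16, while tildrakizumab observation runs to 56 weeks (switched subjects) or 72 weeks (original arm). About 20 of those weeks are off treatment. A table for the overall period, grouped by treatment received and with subjects as denominator, would therefore tend to show more events under tildrakizumab even with equal risk.

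The overall period is also where a reader would look for malignancy, major cardiovascular events and severe infection, which can accrue over the whole follow-up. The readable text gives no person-time denominator for these tables, and SAP 4.8 measures exposure in number of doses.

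**Working it through.** The documents give no adverse event rate or exposure total, so there is no planned figure to reproduce. The check asks what the stated measure would show if there were no true difference.

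**Inputs from the documents.** 107 subjects per arm (SAP 4.2). Part 1 = 16 weeks; Parts 2 and 3 = 72 − 16 = 56 weeks; overall = 72 weeks (SAP 3).

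**Assumptions.** The same constant hazard on placebo and tildrakizumab, full follow-up, and a 16-week risk q. The documents do not give q, so a range is shown.

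**Formula.** Risk over w weeks = 1 − (1 − q)^(w/16). Pooled tildrakizumab is the average of the 56-week and 72-week risks, because the two groups are equal in size.

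For q = 5%: 1 − 0.95^(56/16) = 16.4%; 1 − 0.95^(72/16) = 20.6%; pooled 18.5%; ratio to placebo 3.70.

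| Assumed q | Placebo, 16 wk | Switched, 56 wk | Original arm, 72 wk | Pooled tildrakizumab | Ratio, pooled | Ratio, original arm |
|---|---|---|---|---|---|---|
| 1% | 1.0% | 3.5% | 4.4% | 3.9% | 3.94 | 4.42 |
| 5% | 5.0% | 16.4% | 20.6% | 18.5% | 3.70 | 4.12 |
| 20% | 20.0% | 54.2% | 63.4% | 58.8% | 2.94 | 3.17 |
| 40% | 40.0% | 83.3% | 90.0% | 86.6% | 2.17 | 2.25 |

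In 20,000 simulated trials with no true difference, the crude pooled tildrakizumab percentage exceeded placebo in 87% at q = 0.5%, 95% at q = 1%, and over 99.9% at q = 5% or more.

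**Exposure-adjusted rates.** Under the same assumptions the rate is −ln(1 − q)/16 × 52.18 × 100 per 100 subject-years in every group: 3.28 at q = 1% and 16.73 at q = 5%, so every rate ratio is 1.0. Planned observation is 107 × 16/52.18 = 32.8 subject-years on placebo. Counted under tildrakizumab it is 147.6 (original arm) + 114.8 (switched) = 262.5 before rounding the parts, or 8 times placebo.

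**Other layouts and periods.**
- Part 1: 16 vs 16 weeks, ratio 1.00.
- Parts 2 and 3: continuing subjects all receive tildrakizumab over the same 56 weeks, ratio 1.00.
- Overall by original sequence: 72 vs 72 weeks, ratio 1.00 under no difference. The cost is dilution of a real effect. Take q = 5% on placebo and a true hazard ratio of 2. Over 72 weeks the original arm shows 1 − 0.95^9 = 37.0%. The placebo-then-tildrakizumab sequence shows 1 − 0.95^(1+7) = 33.7%. The ratio is 1.10.

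**Early events.** The distortion depends on hazard staying roughly level. In the extreme case where all risk falls in the first 16 weeks after starting a treatment, each column would read q and the ratio would be 1.00.

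**The case against.** The strongest reply is that the artefact needs a particular layout which the readable text does not fully fix. Former placebo subjects are identified as their own group, the SOC and PT tables may be by arm or in total, and the exposure summary in SAP 4.8 limits the arm split to Part 1. A display by sequence would remove the bias under no difference. This stands in part: the layout is open. But the default columns and denominator in SAP 6.1.4 and 6.1.5, applied to an overall table by treatment received, lead to the unequal comparison. Nothing readable limits the overall adverse event tables as SAP 4.8 limits exposure.

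The redactions also matter. SAP lines 842–847 and 875–890, around the profile, are blacked out, and the protocol's reference to incidence rates may mean person-time rates. A reader might infer that the plan has no exposure adjustment; the documents do not support that.

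A reader might also infer that the Parts 2 and 3 profile carries the same distortion. It does not, because there is no continuing placebo group. The exception is subjects who stop placebo in Part 1 and enter safety follow-up. Shown as placebo, they would have about 20 weeks against 56 (6.2% vs 16.4% at q = 5%), but they are probably few.

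Finally, safety analysis is descriptive, percentages of subjects are the protocol's own safety endpoints, and Part 1 is reported separately with equal nominal follow-up. All of this is correct. It limits the weight of the point but does not make the overall columns comparable.

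**Conclusion.** The concern holds for the overall adverse event profile and the overall severity, relationship and common-TEAE tables. As far as the text can be read, their measure is a crude subject percentage by treatment received. If placebo time is set beside tildrakizumab time, they can show an apparent ratio of about 2 to 4.4 with no true difference. That size rests on equal constant hazards, full follow-up and assumed 16-week risks from 1% to 40%. It shrinks for events that occur early or follow injections, such as injection site reactions, since Part 3 has no study treatment.

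It would go too far to say that the tables will show excess risk. That depends on the columns chosen and on the hazard, and for very rare events chance alone can equalise or reverse the order (about 13% of simulated trials at q = 0.5%). The randomised Part 1 comparison is unaffected. This is a worthwhile, inexpensive improvement to long-term safety reporting.

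**What to change.** Unless the redacted lines already provide it, amend SAP 4.10.1 as follows:

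- State the columns of every overall adverse event table, including where former placebo subjects appear and to which treatment their events are assigned.
- For the overall tables and each AESI, add exposure-adjusted incidence rates: subjects with an event per 100 subject-years at risk, with 95% CI and the subject-years shown.
- For former placebo subjects, split time at risk at the first tildrakizumab injection. State how follow-up after the last dose is counted.
- State that crude percentages are compared between arms in Part 1 only.

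Splitting time in this way avoids both the bias from unequal follow-up and the dilution that comes with display by original sequence.

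The cost is SAP wording and modest extra programming. Dosing records and adverse event start dates are already collected and listed by subject. The limitation is that a single rate assumes a roughly constant hazard, so rates for events that cluster early need to be read with that in mind.

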## 3.0 OBJECTIVES AND ENDPOINTS

Table 1 Study Objectives and Endpoints

Objectives	Endpoints
Primary Efficacy Objective	Primary Efficacy Endpoint

 
To assess the efficacy of tildrakizumab in subjects with moderate to severe scalp psoriasis, as measured by the proportion of subjects who achieve Investigator Global Assessment (IGA) mod 2011 (scalp) score of “clear” and “almost clear” with at least 2-point reduction from Baseline at Week 16.
 
	
 
The proportion of subjects with IGA mod 2011 (scalp) score of “clear” and “almost clear” with at least 2-point reduction from Baseline at Week 16.
 

Primary Safety Objective	Primary Safety Endpoint

 
To assess the safety and tolerability of tildrakizumab in subjects with moderate to severe plaque psoriasis of the scalp [REDACTED] 52 weeks.
 
	
 
The percentage of subjects with incidence, seriousness and severity of all adverse events.
 
The percentage of subjects with severe infections, [REDACTED] whether or not reported as a serious event as per the regulatory definition.
 
The percentage of subjects with malignancies (excluding carcinoma in situ of the cervix).
 
The percentage of subjects with non-melanoma skin cancer.
 
The percentage of subjects with melanoma skin cancer.
 
The percentage of subjects with Major Adverse Cardiovascular Events (MACE).
 
The percentage of subjects with study treatment-related hypersensitivity reactions (eg, anaphylaxis, urticaria, angioedema, etc.).
 
The percentage of subjects with injection site reactions (eg, pain, erythema, edema etc).
 

Secondary Objectives	Secondary Endpoints

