#### **PART 2: Double-blind Active Treatment Extension (Week 16 to Week 52)**

[REDACTED] subjects initially randomized to placebo will be switched over to receive tildrakizumab [REDACTED] while subjects initially randomized to tildrakizumab 100 mg will continue to receive tildrakizumab [REDACTED]. In order to maintain the blind, subjects in both treatment arms will receive matching placebo injections at specified time points as described in the Schedule of Activities (SoA) [REDACTED]

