272 At Week 16, subjects initially randomized to placebo will be switched over to receive
273 tildrakizumab 100 mg [REDACTED] while subjects initially randomized to
274 tildrakizumab 100 mg will continue to receive tildrakizumab [REDACTED]. In
275 order to maintain the blind, subjects who were initially randomized to placebo will receive
276 matching placebo injections [REDACTED] while subjects who were initially
277 randomized to tildrakizumab will receive matching placebo injections at Weeks 20, 32, and
278 44. All assessments of efficacy and safety after the date of injection at Week 16 and before or
279 on the date of injection at Week 52 [REDACTED] [REDACTED] are
280 considered in PART 2.

281 **PART 3: Observational Safety Follow-up (Week 52 to Week 72)**

282 After Week 52 [REDACTED] the study treatment
283 should be stopped and all subjects, including those who terminated early from Part 1 and 2
284 will enter [REDACTED] Observational Safety Follow-up Period to monitor safety and
285 tolerability [REDACTED] following last dose of study treatment. During the follow-up period,
286 subjects should continue on study-approved concomitant medications only, however may be
287 placed on appropriate therapies for safety concerns or significant worsening of psoriasis
288 based on the judgment of the Investigator. The subjects will not receive study treatment
289 during the follow-up period. [REDACTED]
[REDACTED]

292 4 STATISTICAL CONSIDERATIONS OF PROTOCOL

293 4.1 General Statistical Consideration

294 All summaries and analyses conducted will be by assigned therapy and/or combined total
295 subjects. Data obtained on the eCRF and entered into the database will be provided in data
296 listings showing individual subject values.

297 Descriptive statistics (number [n], mean, standard deviation [SD], median, first quartile [Q1],
298 third quartile [Q3], minimum [min], and maximum [max]) for continuous variables and
299 frequency distributions and percentages for discrete variables will be utilized. Categorical
300 variables will be summarized by frequencies and percentages.

301

306 All tabulations of summary statistics, graphical presentations, and statistical analyses will be
307 performed using SAS® Version 9.4 or higher.

308 4.1.1 Baseline and Study Day

309 For purpose of the SAP, Day 1 is defined as the date of first administration of study drug.
310 Study day is calculated relative to the date of Day 1.

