[redacted] placebo-controlled treatment without any major protocol deviation that could impact
393 data interpretability for the primary efficacy endpoint. [redacted]
[redacted]

- [redacted] [redacted]
- [redacted] [redacted]
- [redacted] [redacted]
- [redacted] [redacted]
- [redacted] [redacted]

[redacted]
[redacted]
[redacted]
[redacted]

[redacted]
[redacted]

[redacted]
[redacted]
[redacted]

409 Safety endpoints will be analyzed descriptively based on the SAF, and subjects will be
410 summarized based on the actual treatment they received.

411 **4.5 Protocol Deviations**

412 All protocol deviations (PD) will be tracked throughout the study and classified by deviation
413 type, either minor or major. Protocol deviations represent a failure to adhere to the clinical
414 study protocol. The two types of deviations are defined as:

- 415 • Minor protocol deviation is any change, divergence, or departure from the study
416 design or procedures of a research protocol that has not been approved by the IRB and
417 which does not have a major impact on the subject's rights, safety or well-being, or
418 the completeness, accuracy and reliability of the study data.
- 419 • Major protocol deviation is any change, divergence, or departure from the study
420 design or procedures of a research protocol that has not been approved by the IRB and
421 which has a major impact on the subject's rights, safety or well-being, or the
422 completeness, accuracy and reliability of the study data. [REDACTED]

- [REDACTED] [REDACTED] [REDACTED]
- [REDACTED] [REDACTED] [REDACTED]
- [REDACTED] [REDACTED] [REDACTED]
- [REDACTED] [REDACTED] [REDACTED]
- [REDACTED] [REDACTED] [REDACTED]
- [REDACTED] [REDACTED] [REDACTED]

430 Prior to interim database freeze and final database lock, each deviation will be reviewed to
431 determine if it excludes the patient from any of the analysis sets or any particular planned
432 analysis. These determinations will then be described in the relevant clinical study report.
433 [REDACTED]

434 Minor protocol deviations will be presented as well. All deviations will be retained within
435 the deviations tracker (considered the source document).

436 Protocol deviations attributable to the COVID-19 pandemic regardless whether deemed
437 major or minor will be provided in a separate listing if deemed necessary. Protocol
438 deviations will be presented in summary tables, for IA and overall, respectively.

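### On the visible text of SAP 4.10.1, a Part 2 injection site reaction that follows a blinded placebo injection would be counted under tildrakizumab

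*SAP*

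**What the plan says.** Protocol 3.0 (Table 1) lists among the primary safety endpoints "The percentage of subjects with injection site reactions (eg, pain, erythema, edema etc"). SAP 2.1 sets the primary safety objective over 52 weeks.

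SAP 4.10.1 describes the table: "An AE profile for the Safety Analysis Set will be provided for Part 1, Parts 2 and 3, and" "overall, which summarizes the subject incidence, by treatment received for the following" items. Injection site reactions come first among the adverse events of special interest in that profile. SAP 4.4 says that subjects in the safety set are "summarized based on the actual treatment they received". SAP 6.1.4 gives the column order as placebo, tildrakizumab 100 mg and, where applicable, total. SAP 4.10 adds that former placebo subjects who move to tildrakizumab will be identified as a group for end-of-study reporting.

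On dosing, Protocol 4.1 (Part 2) states: "In order to maintain the blind, subjects in both treatment arms will receive matching placebo injections at specified time points". SAP 3 (Part 2) is more specific. For the original placebo arm, "At Week 16, subjects initially randomized to placebo will be switched over to receive" tildrakizumab, and "order to maintain the blind, subjects who were initially randomized to placebo will receive" matching placebo injections at redacted visits. Subjects originally "randomized to tildrakizumab will receive matching placebo injections at Weeks 20, 32, and" 44.

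SAP 4.10.1 also provides a by-subject listing of injection site reactions and an optional separate summary of them.

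**The concern.** Grouping by regimen suits systemic events. A local reaction belongs to the particular injection that preceded it. In Part 1 each arm receives one product, so regimen and injection content coincide until the Week 16 visit. In Part 2 they do not: the regimen is tildrakizumab for everyone, but some injections contain placebo and are given only to protect the blind.

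What is at stake is the interpretation of a reported long-term safety percentage. Readers will take the Parts 2 and 3 figure, and the overall figure, as the frequency of local reactions to tildrakizumab. Part of it may be reactions to placebo injections. The subset judged drug-related does not separate them, because causality is assessed blind and a missing relationship is treated as related.

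**Working it through.** **Reading the passages together**

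1. Placebo injections are given in Part 2 to both arms (Protocol 4.1; SAP 3). Part 3 has no study treatment, so every injection in the Parts 2 and 3 column is a Part 2 injection, apart from the Week 16 boundary in step 4.
2. The table counts subjects by treatment received (SAP 4.10.1), and no visible column separates injections by content (SAP 6.1.4).
3. So a subject whose only Part 2 reaction follows a placebo injection falls under tildrakizumab. A subject who also reacts to an active injection is counted once either way and adds no excess.
4. SAP 3 (Part 1) places assessments on the date of the Week 16 injection in Part 1, subject to a redaction in that sentence. Former placebo subjects receive tildrakizumab at Week 16. Read literally, a same-day reaction to that first active injection is a Part 1 event and would probably appear under placebo.

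**Size, on assumed inputs**

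The plan has no figure to reproduce. From the documents: 3 placebo visits in the original tildrakizumab arm, and 107 subjects randomised per arm (fewer will reach Part 2). Assumed: k = 2 to 4 active Part 2 injections; reaction risk per active injection pa = 1% to 3%; per placebo injection pp = 0.5% to 2%; independence between injections.

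- Placebo share of Part 2 injections = 3/(3+k): 60%, 50% and 43% for k = 2, 3 and 4.
- Subjects reacting to an active injection = 1 − (1 − pa)^k.
- Subjects reacting to any injection = 1 − (1 − pa)^k × (1 − pp)^3.
- Excess = (1 − pa)^k × [1 − (1 − pp)^3].

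| k | pa | pp | Active only | All injections | Excess (points) | Excess per 107 |
|---|---|---|---|---|---|---|
| 2 | 1% | 2% | 2.0% | 7.8% | 5.8 | 6.2 |
| 3 | 1% | 1% | 3.0% | 5.9% | 2.9 | 3.1 |
| 4 | 1% | 1% | 3.9% | 6.8% | 2.9 | 3.1 |
| 4 | 3% | 0.5% | 11.5% | 12.8% | 1.3 | 1.4 |

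The first and last rows are the extremes of the assumed grid.

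**Clustering**

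Take k = 4 with a 1% mean risk for both products and an assumed intraclass correlation of 0.3 (beta-binomial). Then α = 0.01 × 0.7/0.3 = 0.0233 and β = 0.99 × 0.7/0.3 = 2.31. The probability of no reaction in n injections is the product over i = 0 to n − 1 of (β + i)/(α + β + i). This gives 2.7% over 4 injections and 3.6% over 7. The excess is about 0.9 points, against 2.9 under independence.

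The same calculation cannot be set up for the original placebo arm, because its placebo visits are redacted.

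**The case against.** The strongest reply is redaction. Text is blacked out in SAP 4.10.1 directly after the list of events of special interest, and again earlier in the section, after the rule on relationship to study drug. An attribution rule could be there, and the visible text never defines treatment received for a Part 2 event. This stands: a reader might infer that placebo reactions definitely are counted as tildrakizumab reactions, but the documents support only that they would be on the visible wording.

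Second, the data are not lost. The adverse event listing has start and stop dates, a site-reaction field and time since the most recent dose. Reactions have their own listing, a separate summary is permitted, and SAP 4.8 lists all dosing by subject. A reader might infer that the within-subject comparison of active and placebo injections is forgone; it can still be made after unblinding. What is missing from the visible text is a rule fixed beforehand.

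Third, a reader might infer that the tildrakizumab percentage is inflated by 1.7 to 2 times. Those ratios (6.8/3.9 and 5.9/3.0) come from assuming equal, independent risks per injection. Across the table above the ratio runs from about 1.1 (12.8/11.5) to 3.9 (7.8/2.0), and with clustering it is about 1.35. None of these is evidence from the trial.

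Fourth, the SAP follows the protocol endpoint, which counts subjects. Safety is descriptive, Part 1 is reported separately and holds the randomised comparison, and an over-count in Part 2 runs against the drug. All of this limits the consequence. It does not make regimen-level attribution informative for a local reaction.

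Finally, a reader might take the Part 1 table to be free of the problem. The Week 16 date rule leaves that open.

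**Conclusion.** The point holds as a reporting gap in the visible text. In the Parts 2 and 3 column and the overall column, subjects whose only Part 2 reaction follows a placebo injection would be counted under tildrakizumab, unless a redacted rule says otherwise. The size cannot be derived from the documents. On the assumptions stated, it is about 1 to 6 percentage points in the original tildrakizumab arm, and at a given risk it is smaller if the same subjects tend to react repeatedly. No hypothesis test and no primary efficacy result is affected. The change is worth making because it clarifies a primary safety percentage at little cost.

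**What to change.** In SAP 4.10.1:

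- Classify each injection site reaction by the content of the most recent injection (tildrakizumab or matching placebo), taken from the unblinded kit allocation.
- Keep the planned regimen-level table, and label its Parts 2 and 3 and overall columns as including blinded placebo injections.
- Add one descriptive table with the percentage of subjects who react to a tildrakizumab injection, and the reaction rates per tildrakizumab injection and per placebo injection.
- Apply the same rule at Week 16, so that a same-day reaction to a former placebo subject's first tildrakizumab injection is not counted in Part 1 under placebo.

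The cost is a short paragraph and one extra descriptive table after unblinding. Event dates, dosing records and the central assignment system (Protocol 6.3) should supply the data. If a redacted line already contains such a rule, the sponsor need only confirm it.
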